6 SCREENING /ENROLMENT

Patients will be screened according to the selection criteria (see 5.3.1 and 5.3.2) and the eligibility checklist completed (24.1). Those who meet the selection criteria will be invited to participate in the study. After reviewing the Participant Information form (24.3) and acknowledging that they have understood the purpose of the study, their involvement, risks and benefits, they will be asked to provide written consent (24.3). Any participant who refrains from participation will not be disadvantaged in any way. Any participant who wishes to withdraw during the study of his/her own accord and for whatever reason is entitled to do so without obligation and prejudice. In the event of this occurring, the investigator will record this clearly on the Data Collection Form (24.4).

6.1 STUDY INTERVENTIONS

Following recruitment to the study participants will be booked for surgery. An initial assessment (pre-operative screening test) will be conducted one day prior to surgery. Demographic information will be collected and the initial cognitive screen will be conducted at this assessment. Cognitive assessment will then be repeated at day 1, 10 days post-surgery and at one month and 3 months post-surgery. These time points coincide with standard follow-up intervals post shoulder surgery. Minor changes in the timing of these assessments will be made if necessary to accommodate pre and post-operative surgery schedules.

The intra- operative procedure will be as follows;

1. The patient's bed will be inclined between 30-70 degrees, with the angle being measured by an inclinometer.
2. The anaesthetic and surgical procedure will continue as usual whilst the oximeters record cerebral oxygenation.
3. Any CDE will be recorded on the data collection sheet. Additionally, a digital record will be obtained of mean arterial pressure and also oxygenation from the oximeters until surgery is complete and the patient has regained consciousness. This will allow more detailed analysis by the statistician.
4. Intraoperative drug administration data will be recorded on the data collection sheet (24.4). This will allow for analysis of potential confounding effects.
5. The type of surgical procedure and the duration of surgery will be recorded (24.4) to again reduce further confounding affects.
6. Any variations from the usual surgical/anaesthetic protocol or adverse events will be recorded on the data collection form (24.4).
7. Post-operative analgesia data will be recorded in the data collection form (24.4).

7 DATA COLLECTION

7.1 DATA COLLECTION INTERVALS

Data Collection Interval	Review Method
Baseline (approx. 24 hours prior to surgery)	In person at the clinic
Day 1	In person on the ward
Between 10 and 14 days	In person at the clinic
1 month	In person at the clinic
3 months	In person at the clinic

Data will be collected by an independent assessor who is not involved in the provision of treatment. These data collection points have been chosen to assess both the immediate and longer term effects of cerebral desaturation on cognitive function.

The follow-up period for this study is 3 months. Assessment of cognitive function will be conducted 1 day pre-operatively and as part of routine follow-up appointments at approximately 1 day and 10 days post-op, 1 month and 3 months. In this way we hope to maximise study retention by avoiding the necessity for participants to return for additional appointments beyond those required for normal care.

7.2 DATA COLLECTION FORMS FOR PRIMARY AND SECONDARY OUTCOMES

Clinical and demographic data collection forms will be completed for each participant, and will be performed as per the standard care of the study site. The investigators will perform all of the assessments. Data will be collected on the appropriate paper data collection forms as described below, and later transcribed into electronic databases.

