Monitoring cerebral oxygenation in the BCP is an area of evolving attitudes in regards to standard of care. There are many hospitals in Australia who have now adopted cerebral oximetry as a standard of care for monitoring patients in the beach chair position. It is the feeling of all of the surgeons involved in the investigation that in fact, cerebral oxygenation monitoring is part of an adequate standard of care for patients in the beach chair position and it is routinely utilised currently in all beach chair position surgeries. It is not expected that there will be any significant alteration to operative time by placing two oxygen monitors and there is certainly no risk to the surgeon, anaesthetist or the nursing team. Data is recorded using monitors that output the data digitally and all of the data will be compared using standard timestamp methods so that they can be directly compared. The oximetry and MAP data will be simultaneously digitally recorded for the research data collection and analyses.

In conclusion, the relationship between shoulder surgery in the BCP and cerebral oxygenation is suggestive and requires further investigation. In addition, factors associated with cerebral desaturation and the incidence of POCD are not well understood. The value of cerebral oximetry in predicting CDE and POCD remains unclear. Further research in these areas is indicated and the proposed study aims to address the issues raised here.

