2.2 LAYMAN'S SUMMARY

Surgery to the shoulder may be performed with patients seated upright in a position known as the “Beach Chair Position (BCP).” This position has certain advantages compared to alternative surgical positions (eg side lying) in some situations. However, it has been found that surgery in the BCP can temporarily decrease the amount of oxygen in the brain as a result of the combined effects of gravity and anaesthesia. This can result in complications following surgery such as some memory loss and confusion. Rarely, more serious complications have been reported in the past including death and stroke.

Due to these reported complications the use of “cerebral oximetry” during shoulder surgery in the BCP has become more common. Before and during surgery, a monitor placed on the patients forehead measures the amount of oxygen present in the brain to help control this to an acceptable level. A number of monitors are now commercially available. Two monitors are commonly discussed in the literature; the INVOS™ 5100 and the FORE-SIGHT® machines. However, the actual relationship between the supply of oxygen to the brain

during surgery and the chance of later developing problems with memory and thinking (known as “post operative cognitive decline” – POCD) is not clear. It is also not known if one monitor is more accurate than another at predicting these complications.

Therefore, the main aim of this study is to examine the relationship between cerebral oxygen levels during shoulder surgery and the incidence of POCD (i.e. problems with memory and thinking). A second aim is to compare the INVOS™ 5100 and FORE-SIGHT® monitors ability to measure cerebral oxygen and CDE as well as the importance of other key clinical variables (e.g. blood pressure, nausea, body fat etc).

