5 STUDY DESIGN AND METHODS

5.1 GENERAL

This study aims to examine the relationship between cerebral desaturation measured via oximetry during shoulder surgery in the BCP, and POCD. Patients treated by the Principal Investigators who meet the selection criteria, will be invited to participate in this prospective study. The investigation will be conducted at the Brisbane Hand and Upper Limb Research Institute at the Brisbane Private Hospital, Brisbane, Australia.

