5.4 RECRUITMENT

The study patient population will be recruited primarily from the private consulting practices of the Principal investigators at the Brisbane Hand and Upper Limb Clinic at the Brisbane Private Hospital. All patients who are undergoing surgery in the beach chair position will be approached by a member of the research team or a research assistant employed by BHULI after they have indicated to the consultant their interest in participating in the study after the decision to undertake surgery has been made. Indeed all patients who are undergoing shoulder surgery in beach chair position by any of the surgeons involved the study would be undergoing surface cerebral oximetry anyway. There is no question that the discussion regarding participating in the study would not happen until it was already established that the patient was undergoing shoulder surgery in the beach chair position. It has nothing to do with the clinical discussion regarding the patient's treatment.

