11 RISK ANALYSIS

Shoulder surgery in the BCP is routinely used in clinical practice. Participants who agree to be part of the trial will experience no additional risks above those normally associated with this routine procedure. X-ray imaging is performed for some surgical procedures as the normal course of intraoperative patient care. Suspected adverse neurological outcomes associated with the surgery may require further imaging in the form of cerebral CT / MRI as is standard practice. Such imaging would be unrelated to the monitoring of cerebral oximetry.

If a participant is found to be experiencing psychological distress (i.e. depression, anxiety or suicidality) or is found to have a significant cognitive impairment, the following procedures will be put in place. Psychological distress will be monitored initially through the psychological measures being used and will be administered by a clinical psychology trainee or other health professional. These measures are standardised and have recognised clinical cut-off criteria. The medical consultant in the project team will be informed of anyone meeting the criteria for at least mild to moderate levels of distress. As the medical consultant is responsible for the care of all patients, he will take responsibility for any onward referral or medical management as per standard clinical practice. A similar procedure will be followed in the case of significant cognitive impairment. The neuropsychological tests are standardised with norms provided to indicate possible impairment. The medical consultant will be informed of anyone meeting the criteria for mild to moderate impairment and this will be managed as per standard clinical practice with referral for further assessment. Additionally, any mood- or cognitive-related concerns raised by participants will be brought to the attention of the medical consultant.

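### Nothing masks the cognitive tester to oximetry or desaturation data, and sections 4, 7.1 and 7.2 leave open who the tester is

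*Protocol*

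**What the plan says.** Four parts of the protocol bear on who measures the primary outcome and what that person may know.

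- **Section 7.1:** "Data will be collected by an independent assessor who is not involved in the provision of treatment". No other condition is attached to the role.
- **Section 7.2**, whose heading covers the primary and secondary outcomes: "The investigators will perform all of the assessments".
- **Section 4** lists, among the investigators' duties, delivering the intervention and gathering both the intra-operative measurements and the cognitive results. Section 5.1 adds: "Patients treated by the Principal Investigators who meet the selection criteria, will be invited to participate in this prospective study".
- **Sections 6.1 and 8.2** have each CDE written on the data collection sheet or form. Section 7.2.3 says the participant's form (24.4) also carries the outcome data, and section 8.4 has form 24.4 used for adverse events at every assessment.

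On timing, section 6.1 says: "An initial assessment (pre-operative screening test) will be conducted one day prior to surgery". Section 11 says the psychological measures "will be administered by a clinical psychology trainee or other health professional". It does not name who gives the cognitive tests. The randomisation and counterbalancing in the protocol concern sensor position and test packages, not what the tester knows.

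**The concern.** The primary hypothesis is that CDEs are related to POCD. POCD is derived from tests that an examiner gives and scores face to face. If the examiner knows which patients desaturated, prompting, timing and scoring decisions can differ between the groups being compared.

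The pre-operative test cannot be affected, because no CDE has yet happened. Any influence therefore falls on the post-operative scores alone and enters the change from baseline on which POCD is judged. The planned regression cannot remove it, because tester knowledge is not among the variables the protocol describes recording.

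This is a matter of study conduct, so a statistical analysis plan could not repair it. Masking that was absent at testing cannot be restored afterwards.

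**Working it through.** **1. The sections side by side**

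| Question | 7.1 | 7.2 | 4 |
|---|---|---|---|
| Who collects or assesses? | Independent assessor | Investigators, all assessments | Investigators |
| May that person treat? | No | Not addressed | Same group delivers the intervention |
| May that person know CDE status? | Not addressed | Not addressed | Same group gathers intra-operative data |

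A non-treating investigator would satisfy both 7.1 and 7.2, but only 7.1 asks for someone outside treatment. None of the three addresses knowledge of CDE status.

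**2. Routes by which the tester could learn the exposure**

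- Section 4 puts exposure and outcome data in the same group's hands.
- CDEs and outcomes go on one participant form (6.1, 7.2.3, 8.2), which is in use at each visit (8.4). Most of form 24.4 is not available to us, so whether its pages are already separate cannot be checked.

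**3. The plan's own sample size (section 10.1)**

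Inputs: p1 = 0.29, p2 = 0.50, share without CDE 62%, so k = 0.38/0.62 = 0.613; alpha 0.05 (two-sided assumed), power 80%. Pooled p = 0.62×0.29 + 0.38×0.50 = 0.3698.

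n1 = [1.960×√(0.3698×0.6302×(1+1/k)) + 0.8416×√(0.29×0.71 + 0.25/k)]² / 0.21² = (1.535 + 0.659)² / 0.0441, which rounds up to 110.

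The total is 110 + 68 = 178 without continuity correction and 122 + 75 = 197 with it. The stated 193 is close to the corrected figure, so 193 is a fair base for an illustration.

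**4. Illustration: how much misclassification makes a null result significant?**

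Assume N = 193, true POCD 29% in both groups, and k CDE patients without POCD wrongly scored as having it. The CDE share is 38% (section 10.1) or 18% (the earlier shoulder study described in section 2). Counts are rounded to whole patients.

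| CDE share | Start | k | Result | RR | p, uncorrected | p, Fisher |
|---|---|---|---|---|---|---|
| 38% | 21/73 v 35/120 | 10 | 31/73 | 1.46 | 0.059 | 0.063 |
| 38% | | 11 (of 52, 21%) | 32/73 | 1.50 | 0.038 | 0.044 |
| 18% | 10/35 v 46/158 | 6 | 16/35 | 1.57 | 0.057 | 0.072 |
| 18% | | 7 (of 25, 28%) | 17/35 | 1.67 | 0.026 | 0.030 |

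For k = 11: chi-square = 193×(32×85 − 41×35)² / (73×120×67×126) = 193×1285²/73,951,920 = 4.31, p = 0.038. With continuity correction, 193×(1285 − 96.5)²/73,951,920 = 3.69, p = 0.055. The threshold at a 38% share therefore depends on the test used.

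Each patient moved raises the risk ratio by (1/73)/(35/120) = 0.047 at a 38% share, or (1/35)/(46/158) = 0.098 at 18%.

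**5. Illustration: false-positive rate**

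Suppose instead that the observed POCD risk in the CDE group rises by d points (38% share, normal approximation, two-sided 0.05). N = 140 is 200 less the 30% loss in section 5.5.

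| d | N = 193 | N = 140 |
|---|---|---|
| 0 | 5.0% | 5.0% |
| 2 points | 6.1% | 5.8% |
| 5 points | 11.5% | 9.8% |
| 10 points | 30.3% | 23.4% |

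The values of d are assumptions. Nothing in the protocol indicates which, if any, applies.

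**The case against.** The strongest reply is that 7.1 already provides an independent assessor and nothing in 7.2 cancels that rule. The 7.2 sentence follows one about clinical and demographic forms, so it may be meant narrowly. Section 11 also makes a tester from outside the surgical team plausible. This stands in part: a reader might infer that 7.1 and 7.2 flatly contradict each other, and they do not. But independence from treatment is not masking to exposure, and 7.2 speaks of all assessments under a heading that includes the primary outcome.

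A reader might also infer from the routine clinical use of oximetry that the tester will know the readings. The protocol says of oximetry that "it is routinely utilised currently in all beach chair position surgeries", that these surgeons' patients "would be undergoing surface cerebral oximetry anyway", and that a monitor "measures the amount of oxygen present in the brain to help control this to an acceptable level". Those statements concern the treating team or describe oximetry in general. They bear on the tester only if a member of that team does the testing. No text says the assessor sees the data.

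The outcome itself gives some protection. The tests are structured, versions alternate in counterbalanced order, and POCD needs a fall of at least 1 SD on at least two indices. A small examiner effect changes POCD status only for patients near that threshold. CDE is a numeric criterion backed by a digital record. These features limit the bias without removing it.

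Finally, the illustrations move patients in one direction only, while the true direction is unknown and could be towards no association. That objection is correct, and it is why severity does not rest on them.

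**Conclusion.** The point holds as a gap in masking combined with unclear wording on who tests. As written, the plan allows someone who knows CDE status to give and score the primary outcome, and sections 4 and 7.2 do not repeat the one safeguard in 7.1.

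The documents do not support concluding that testers will in fact be unmasked, that the surgeons will do the testing, or that a positive result would be spurious. For a false positive to arise from this source alone, roughly a fifth to over a quarter of unaffected CDE patients (21% to 28%) would have to be misclassified in the same direction. Smaller effects could still shift the estimate.

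This rests on three assumptions: that form 24.4 does not already separate its pages, that no text withheld from review states masking, and, for the illustrations, the 29% POCD rate and the 38% or 18% CDE share. Severity is low to moderate. The case for acting is that the remedy is cheap and cannot be applied after testing.

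**What to change.** Amend three sections together.

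- **7.1:** state that the independent assessor, who is not involved in treatment and may be a non-treating investigator, gives and scores all cognitive tests, and gives the psychological measures and pain scale, at every visit, without access to oximetry, CDE or intra-operative records until that participant's 3-month tests are scored.
- **7.2:** replace the sentence on investigators with one saying that cognitive, psychological and pain assessments are performed by the independent assessor (7.1), and that intra-operative data are recorded by the treating team.
- **4:** make the list of investigator duties consistent with this split.

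If form 24.4 is not already divided, keep its intra-operative and CDE pages away from the assessor and link the parts by study number after scoring. The section 11 notice to the medical consultant can stay, because that information flows from the tester to the consultant.

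**Cost:** an ethics amendment and a little form handling. The assessor is already planned in 7.1, and the section 12 budget lists a research assistant and study assessments in kind. Because the summary of changes records a team leaving the project, confirm that the role is filled. If testing has begun, participants assessed before the amendment cannot be masked and should be flagged in the data.

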7.2.1 ELIGIBILITY CRITERIA CHECKLIST

An Eligibility Criteria Checklist will be completed prior to seeking informed voluntary consent (24.3).

7.2.2 DEMOGRAPHIC AND MEDICAL INFORMATION FORM

Demographic and medical information will be obtained from each participant who is recruited to the study (see 15.4). This information will include, but is not limited to:

- Age
- Gender
- Occupation

- Information pertinent to surgery and/or neuropsychological assessment (e.g. recreational activities)
- Current medical status (e.g. diagnosis, side of injury) and co-morbidities (e.g. diabetes mellitus)
- Medical History e.g. cerebrovascular disease, hypertension
- History of current and previous medication, supplements

7.2.3 DATA COLLECTION FORMS FOR PRIMARY AND SECONDARY HYPOTHESES

Primary and secondary outcomes will be recorded for each participant on their data collection form. This form will include demographic, clinical and outcome data (24.4). The primary outcome to be measured is the incidence of Post-operative Cognitive Decline. This has been defined as a drop of 1 standard deviation or more from baseline on 2 or more of the neuropsychological indices included. The secondary outcome to be measured is the incidence of cerebral desaturation as well as the importance of other key clinical variables (e.g. blood pressure, nausea, body fat etc).

8 OUTCOME MEASURES

8.1 COGNITIVE ASSESSMENT TOOLS

8.1.1 NEUROPSYCHOLOGICAL TESTS

Logical Memory (5 minutes) - impairment in perceptions of and/or psychometrically determined, immediate and delayed recall and recognition memory following surgery has been frequently noted in research examining POCD (Krenk et al., 2010; Salazar et al., 2013). Commonly used psychometrically viable tests are prose story memory recall and recognition tests. The prose story is administered at the beginning of the session and the immediate recall occurs straight after. Delayed recall for the story occurs after 20-30 minutes. The test-retest reliability, construct and convergent validity of this test has been proven time again, commonly rendering an adequate to good coefficient (Sullivan, 2005).

Trails: Delis-Kaplan Executive Function System (10 minutes) - The D-KEFS was designed to detect even mild forms of executive dysfunction (Strauss et al., 2006). Executive dysfunction has been inadvertently linked with significant post-operative cognitive declines following surgery (Krenk, et. al., 2010). The D-KEFs Trails subtest has four trials; visual scanning, number sequencing, letter sequencing and letter number sequencing. The internal and test-retest reliability, and convergent and predictive validity of the D-KEFS is consistently adequate to high, and this subtest in particular renders a good to high coefficient (Strauss, et al., 2006).

Single Letter Verbal Fluency (1 minute) - Performance on brief verbal fluency tasks have been found to change pre- to post- surgery following cerebral desaturation events (Salazar et al., 2013). Aside from being a suitable assessment of both premorbid and current intellectual performance, tasks of verbal fluency examine spontaneous production of language and verbal associations. The task requires the individual to spontaneously generate a list of words in 60 seconds, where the words cannot be name of places, people or other proper nouns. A one-letter task is administered per package and has been found to be as valid as a three-letter fluency task (i.e. FAS or PGH;

Strauss, et al., 2006). Verbal fluency tasks have been found to have high internal and test-retest reliability and adequate to high content, construct and predictive validity (Strauss, et al., 2006).

Stroop Test Victoria's Version (5 minutes) - The stroop task has three components. The first examines colour discrimination, selective attention and visual scanning. The second assesses word discrimination and selective attention. The third examines the ability to inhibit responses and cognitive flexibility, it requires an individual to verbalise the colour the word is written in, when the words are colours. This version of the Stroop test was selected for the purposes of large font size, a brief amount of items in comparison to other versions thus requiring less administration time. The reliability of the test is adequate and the test itself has been found to be sensitive enough to detect changes from baseline (Strauss, et al., 2006).

List Learning – Rey Auditory Verbal Learning Test (RAVLT; 5-10 minutes) - Performance on a brief list-learning task has been found to change pre- to post- surgery following cerebral desaturation events (Salazar et al, 2013). Due to the poor validity and reliability of such a brief task, however, a full list-learning task is designed to be more sensitive to change as well as having a greater validity and reliability (Strauss, et al., 2006). The RAVLT assesses immediate and delayed auditory memory recall and recognition. The task consists of 15 nouns learned over 5 trials with a free recall after each presentation. The order of presentation remaining fixed across trials (List A). At the end of the 5th trial an interference list of 15 words is presented (List B), following a free recall of that list. Immediately after this, delayed recall of the first list is tested. Following a 20-minute delay, delayed recall and recognition of the first word list is assessed.

Letter-Number Sequencing (from Wechsler Adult Intelligence Scale, fourth edition subtest (WAIS-IV), 5-10 minutes) - This particular subtest of the WAIS-IV assesses attention and concentration. The examinee is verbally presented with a combination of numbers and letters or increasing amounts. The examinee is required to recall the numbers in ascending order then letters in alphabetical order. The WAIS-IV as an overall measure is one of the most widely used tests of intelligence and has consistently rendered highly valid and reliable results. This subtest of the WAIS-IV has high internal consistency and adequate test-retest reliability (Strauss, et al., 2006; Wechsler, 2008).

